8.4 Dexamethasone Dose Modifications

Table 8.41: Dose Modifications for Dexamethasone

NCI CTC Category	Adverse Event	Dosage Change
Gastrointestinal	Dyspepsia, gastric or duodenal ulcer, gastritis Grade 1-2 (requiring medical management)	Treat with H ₂ blockers, sucralfate, or omeprazole. If symptoms persist despite above measures, decrease dexamethasone dose by 1 dose level.
	≥Grade 3 (requiring hospitalization or surgery)	Hold dexamethasone until symptoms adequately controlled. Restart by decreasing dose by 1 dose level along with concurrent therapy with H ₂ blockers, sucralfate, or omeprazole.
	Acute pancreatitis	Discontinue dexamethasone and do not resume.
Cardiovascular	Edema ≥Grade 3 (limiting function and unresponsive to therapy or anasarca)	Diuretics as needed, and decrease dexamethasone dose by 1 dose level.
Neurology	Confusion or Mood alteration ≥Grade 2 (interfering with function +/- interfering with activities of daily living)	Hold dexamethasone until symptoms adequately controlled. Restart by decreasing dose by 1 dose level.
Musculoskeletal	Muscle weakness ≥Grade 2 (symptomatic and interfering with function +/- interfering with activities of daily living)	Decrease dexamethasone dose by 1 dose level. If weakness persists decrease dose by 1 dose level as needed.
Metabolic	Hyperglycemia ≥Grade 3 or higher	Treatment with insulin or oral hypoglycemics as needed. If uncontrolled despite above measures, decrease dose by 1 dose level.
Any Other	≥Grade 3 or higher	Hold dexamethasone until symptoms adequately controlled. Restart by decreasing dose by 1 dose level.

Table 8.42: Dexamethasone Dose Levels

	Dosage	Days
Starting Dose	40 mg	Days 1, 8, 15, 22
Dose Level -1	20 mg	Days 1, 8, 15, 22
Dose Level -2	20 mg	Days 1,15 only
Dose Level -3	10 mg	Days 1, 15 only
Dose Level -4		Discontinue Dexamethasone

9.0 Ancillary Treatment

9.1 Growth Factors:

9.11 Erythropoietin (Procrit or Aranesp) may be used to treat anemia beginning in treatment cycle 2 at the discretion of the treating physician in accordance with the published ASCO/ASH guidelines (JCO 2002, 20: 4083-4107).

9.12 G-CSF/GM-CSF: G-CSF/GM-CSF may be used beginning in treatment cycle 2 in accordance with published NCNN guidelines (see Section 8.0 Treatment Modification Based on Toxicity).

9.2 Infection Prophylaxis: Ciprofloxacin or Levofloxacin daily (or other quinolone/broad spectrum antibiotic) is allowed.

The dose of ciprofloxacin should be modified in impaired renal function as follows:

- 250 to 500 mg every 12 hours for creatinine clearance between 30 to 60 mL/min
- 250 to 500 mg every 18 hours for creatinine clearance between 5-29 mL/min

The dose of levofloxacin should be modified in impaired renal function as follows:

- 250 mg every 24 hours for creatinine clearance between 20-49 mL/min
- 250 mg every 48 hours for creatinine clearance between 10-19 mL/min

9.3 GI Toxicity: Routine prophylaxis with H₂ blockers or proton pump inhibitors should be considered for all patients during days of dexamethasone administration.

9.4 Anti-Coagulation: Lenalidomide increases the risk of thrombotic events in patients who are at high risk or with a history of thrombosis, in particular when combined with other drugs known to cause thrombosis. When lenalidomide is combined with other agents such as steroids (e.g., dexamethasone, prednisone), anthracyclines (Doxil, Adriamycin) and erythropoietin the risk of thrombosis is increased. Prophylactic anti-coagulation with aspirin (ASA) is required for all patients at either 81 mg daily or 325 mg daily (dose per MD discretion). Heparin, low molecular weight heparin or coumadin may be utilized in patients that are intolerant to ASA. Coumadin should be used with caution and close monitoring of INR.

9.5 Any other supportive measures consistent with optimal patient care should be given throughout the study.

10.0 Adverse Event (AE) Monitoring and Reporting

Adverse Event (AE) is defined as any new untoward medical occurrence or worsening of a pre-existing medical condition in a patient administered a medicinal product in a clinical investigation and which does not necessarily have a causal relationship with this treatment. An AE can therefore be any unfavorable and unintended sign (e.g., including an abnormal laboratory finding), symptom, or disease temporally associated with the use of a product (investigational or marketed), whether or not considered related to the product (investigational or marketed).

Following written consent to participate in the study, the collection of AEs/SAEs should begin at the initiation of therapy, unless related to a protocol related procedure.

10.1 Toxicity will be scored using CTCAE Version 4.0 for toxicity and adverse event reporting. A copy of the CTCAE Version 4.0 can be downloaded from the CTEP homepage (<http://ctep.info.nih.gov>). All appropriate treatment areas should have access to a copy of the CTCAE Version 4.0. All adverse clinical experiences, whether observed by the investigator or reported by the patient, must be recorded, with details about the duration and intensity of each episode, the action taken with respect to the test drug, and the patient's outcome. The investigator must evaluate each adverse experience for its relationship to the test drug and for its seriousness.

The investigator must appraise all abnormal laboratory results for their clinical significance. If any abnormal laboratory result is considered clinically significant, the investigator must provide details about the action taken with respect to the test drug and about the patient's outcome.

10.11 Assessment of Attribution

When assessing whether an adverse event is related to a medical treatment or procedure, the following attribution categories are utilized:

Definite: The adverse event *is clearly related* to the investigational agent(s).
Probable: The adverse event *is likely related* to the investigational agent(s).
Possible: The adverse event *may be related* to the investigational agent(s).
Unlikely: The adverse event *is doubtfully related* to the investigational agent(s).
Unrelated: The adverse event *is clearly NOT related* to the investigational agent(s).

10.12 When a study includes both investigational and commercial agents, the following apply:

- When an investigational agent(s) is used in combination with a commercial agent(s), the combination is considered investigational. Reporting of adverse events follows the guidelines for investigational agents.

10.2 All Adverse Events are to be graded at each evaluation and all pretreatment symptoms/conditions are to be evaluated at baseline per Common Terminology Criteria for Adverse Events (CTCAE) Version 4.0 grading. The specific Adverse Events/Symptoms in the table below are to be collected as indicated below:

Category	Adverse Event/Symptoms	Baseline	Each Evaluation
Blood/Bone Marrow	Hemoglobin	X	X
	Neutrophils/Granulocytes (ANC/AGC)	X	X
	Platelets	X	X
Constitutional Symptoms	Fatigue (lethargy, malaise, asthenia)	X	X
Neurology	Neuropathy-Sensory	X	X
Dermatology/Skin	Rash/Desquamation	X	X
Renal/Genitourinary	Cystitis	X	X
Lymphatics	Edema: Limb	X	X
Gastrointestinal	Nausea	X	X
	Vomiting	X	X
	# of stools per day	X	
	Diarrhea		X
Musculoskeletal/Soft Tissue	Muscle Weakness/Lower Extremity	X	X

10.21 Submit via appropriate electronic Case Report Forms (eCRFs) the following AEs experienced by a patient and not specified in Section 10.2. If known, the diagnosis of the underlying illness or disorder should be recorded, rather than individual symptoms. The following information should be documented for all AEs: date of onset and resolution, severity of the event; the investigator's opinion of the relationship to investigational product; treatment required for the AE; cause of the event (if known); and information regarding resolution/outcome.

- Grade 1 and 2 AEs deemed *possibly, probably, or definitely* related to the study treatment or procedure.
- Grade 3 and 4 AEs regardless of attribution to the study treatment or procedure
- Grade 5 AEs (Deaths)
 - Any death within 30 days of the patient's last study treatment or procedure regardless of attribution to the study treatment or procedure.

- Any death more than 30 days after the patient's last study treatment or procedure that is felt to be at least possibly treatment related must also be submitted as a Grade 5 AE, with a CTCAE type and attribution assigned.

10.22 Refer to the instructions in the eCRF Study Manual regarding the submission of late occurring AEs following completion of the Active Monitoring Phase (e.g., compliance with Test Schedule in Section 4.0).

10.3 Serious Adverse Event (SAE) Definition

A serious adverse event is one that at any dose (including overdose):

- Results in death
- Is life-threatening¹
- Requires inpatient hospitalization or prolongation of existing hospitalization
- Results in persistent or significant disability or incapacity²
- Is a congenital anomaly or birth defect
- Is an important medical event³
- Diagnosis of new second primary cancer

¹ “Life-threatening” means that the subject was at immediate risk of death at the time of the serious adverse event; it does not refer to a serious adverse event that hypothetically might have caused death if it were more severe.

² “Persistent or significant disability or incapacity” means that there is a substantial disruption of a person’s ability to carry out normal life functions.

³ Medical and scientific judgment should be exercised in deciding whether serious adverse event reporting is appropriate in situations where none of the outcomes listed above occurred. Important medical events that may not be immediately life-threatening or result in death or hospitalization but may jeopardize the patient or may require intervention to prevent one of the other outcomes listed in the definition above should also usually be considered serious. Examples of such events include allergic bronchospasm requiring intensive treatment in an emergency room or at home, blood dyscrasias or convulsions that do not result in inpatient hospitalization, or the development of drug dependency or drug abuse. A new diagnosis of cancer during the course of a treatment should be considered as medically important.

10.31 The investigator must appraise all abnormal laboratory results for their clinical significance. If any abnormal laboratory result is considered clinically significant, the investigator must provide details about the action taken with respect to the test drug and about the patient’s outcome.

10.32 Pregnancies

Prior to study enrollment, women of childbearing potential (WOCBP) must be advised of the importance of avoiding pregnancy during trial participation and the potential risk factors for an unintentional pregnancy, documented in the informed consent. In addition, all WOCBP should be instructed to contact the Investigator immediately if they suspect they might be pregnant (e.g., missed or late menstrual period) at any time during study participation.

Pregnancy of a female subject or the female partner of a male subject occurring while the subject is on lenalidomide or within 4 weeks after the subject's last dose of lenalidomide are considered expedited reportable events. If the subject is on lenalidomide, it is to be discontinued immediately and the subject is to be instructed to return any unused portion of lenalidomide to the Investigator. The pregnancy must be reported to PrECOG within 24 hours of the Investigator's knowledge of the pregnancy by phone and facsimile using the Pregnancy Form. Within 24 hours of notification, PrECOG will fax to Celgene Drug Safety the Pregnancy Form.

- The Investigator will follow the pregnant female until completion of the pregnancy, and must notify PrECOG of the outcome as specified below. PrECOG will provide Celgene Drug Safety with the outcome. The Investigator will provide this information as a follow-up to the initial submission.
- If the outcome of the pregnancy meets the criteria for immediate classification as a SAE (e.g., spontaneous abortion [any congenital anomaly detected in an aborted fetus is to be documented], stillbirth, neonatal death, or congenital anomaly), the Investigator should follow the procedures for Expedited Reporting of SAEs to PrECOG (e.g., report the event to PrECOG by facsimile within 24 hours of the Investigator's knowledge of the event). PrECOG will report the event to Celgene Drug Safety within 1 business day of the knowledge of the event.
- Any suspected fetal exposure to lenalidomide must be reported to PrECOG within 24 hours of being made aware of the event. PrECOG will report any suspected fetal exposure to Celgene Drug Safety within 1 business day of being aware of the event. The pregnant female should be referred to an obstetrician/gynecologist experienced in reproductive toxicity for further evaluation and counseling.
- All neonatal deaths that occur within 30 days of birth should be reported, without regard to causality, as SAEs. In addition, any infant death after 30 days that the Investigator suspect is related to the *in utero* exposure to lenalidomide should also be reported.
- In the case of a live "normal" birth, PrECOG should be advised as soon as the information is available. PrECOG will advise Celgene Drug Safety as soon as the information is available.

10.4 Serious Adverse Event Reporting by Investigator to PrECOG

10.41 Serious adverse events (SAE) are defined above. The investigator should inform PrECOG of any SAE within 24 hours of being aware of the event. The date of awareness should be noted on the report. This must be documented on PrECOG SAE form. This form must be completed and supplied to PrECOG within 24 hours/1 business day at the latest on the following working day. The initial report must be as complete as possible, including details of the current illness and (serious) adverse event, and an assessment of the causal relationship between the event and the investigational product(s). Information not available at the time of the initial report (e.g., an end date for the adverse event or laboratory values received after the report) must be documented on a follow-up PrECOG SAE report form. A final report to document resolution of the SAE is required. A copy of the fax transmission confirmation of the SAE report to PrECOG should be attached to the SAE and retained with the patient records.

PrECOG Drug Safety Contact Information

All SAEs should be faxed to:

[contact]

as per the instructions found in study materials provided to the investigator site.

████████████████████
Medical Monitor
During Normal Business Hours
8:30 am-5:00 pm EST
[contact]
After Normal Business Hours
[contact]
████████████████████

Manager, Clinical Safety
During Normal Business Hours
8:30 am-5:00 pm EST
[contact] ext 143
After Normal Business Hours
[contact]

PrECOG will notify Celgene of any SAE within 1 business day of receipt from the site.

Collection of complete information concerning SAEs is extremely important. Full descriptions of each event will be followed. Thus, follow-up information which becomes available as the SAE evolves, as well as supporting documentation (e.g., hospital discharge summaries and autopsy reports), should be collected subsequently, if not available at the time of the initial report, and immediately sent using the same procedure as the initial SAE report.

All SAEs must be collected which occur within 30 days of discontinuation of dosing for lenalidomide and/or dexamethasone, whichever is the last to be received. In addition, the Investigator should notify PrECOG or designee of any SAE that may occur after this time period which they believe to be definitely, probably or possibly related to investigational product.

10.5 Reporting of Other Second Primary Malignancies

All cases of new primary malignancies that occur on PrECOG protocols during or after protocol treatment must be reported as a SAE and documented on a PrECOG SAE form. New primary malignancies should be reported within 24 hours of being aware of diagnosis, regardless of relationship to protocol treatment. SAE submission process described above in Section 10.4 should be followed. A copy of the pathology report should be sent with SAE form, if available.

NOTE: Data regarding survival and remission status, second primary malignancies, and recurrence of prior malignancies will be followed x 3 years. This should include subjects who may have discontinued the study at any time or for any reason, who may be in a survival follow-up period, or who may have died. Data for all identified cases of subsequently diagnosed second primary malignancies after this 3 year time will be reported voluntarily by the treating physician to the manufacturer.

11.0 Treatment Evaluation

(Response is to be assessed at the end of each treatment cycle within 3 days prior to the start of the next cycle)

11.1 Terms and Definitions

- **M-Protein:** synonyms include M-spike, monoclonal protein and myeloma protein, paraprotein, M-component.

Serum M-protein level is quantitated using densitometry on SPEP except in cases where the SPEP is felt to be unreliable.

- M-proteins migrating in the β -region (usually IgA M-proteins)
- Cases in which the M-spike is so large and narrow on agarose (some specimens >4 g/dL) that they underestimate the actual immunoglobulin (Ig) level (by greater than 1500 mg/dL) due to technical staining properties of the agarose gel
- Cases in which there are multiple peaks of same monoclonal protein (aggregates or dimers)

If SPEP is not available or felt to be unreliable (above examples) for routine M-protein quantitation, then quantitative immunoglobulin levels derived from nephelometry or turbidometry can be accepted. However, this must be explicitly reported at baseline, and only nephelometry can be used for that patient to assess response. SPEP derived M-spike values and quantitative nephelometric immunoglobulin values cannot be used interchangeably. In determining response, if the quantitative immunoglobulin result contradicts the M-spike result (or vice-versa), the treating physician may request permission from the PI to alter which parameter will be followed for response determination. This adjustment may be made once during a patient's course.

Urine M-protein measurement is estimated using 24-h UPEP only. Random or 24-h urine tests measuring kappa and lambda light chain levels are not reliable and are not accepted for this study.

Free light chain (FLC) estimation is currently carried out using the serum FLC assay (Freelite, The Binding Site Limited, UK). Patients with kappa/lambda FLC ratio <0.26 are defined as having monoclonal lambda FLC and those with ratios >1.65 as having a monoclonal kappa FLC. The monoclonal light chain isotype is considered the involved FLC isotype, and the opposite light chain type as the uninvolved FLC type.

- **Response Terms:** The following response terms will be used: stringent Complete Response (sCR), complete response (CR), very good partial response (VGPR), partial response (PR), stable disease (SD), progressive disease (PD) and relapse from CR (RFCR).

In addition, for each response category, there will be an “unconfirmed” response category, which will be for internal use, for the purpose of guiding decision making and test ordering. These designations will be applied at the time of the first measurement at which the quantitative aspect of the response category has been satisfied without the confirmation step having been satisfied. The designation “u” will precede the standard abbreviations, and will include usCR, uCR, uVGPR, uPR, uPD.

- **Measurable Disease:** Patients who have a measurable serum or urine M-protein.
 - Serum M-protein ≥ 1 g/dl
 - Urine M-protein ≥ 200 mg/24 h
 - Serum FLC assay: Involved FLC level ≥ 10 mg/dl provided serum FLC ratio is abnormal
 - Bone marrow plasma cells $\geq 30\%$

The serum free light chain (FLC) assay is of particular use in monitoring response to therapy in patients who have oligo-secretory or non-secretory disease and **should be used in assessing response only if the baseline serum and/or urine M proteins are not “measurable” as above, and the baseline level of the involved FLC is “measurable.”** When using this assay, it is important to note that the FLC levels vary considerably with changes in renal function and in patients with renal insufficiency, the levels of both the kappa and lambda may remain elevated, but the ratio normalizes with achievement of CR. Thus both the level of the involved and the uninvolved FLC isotype (e.g., the involved/uninvolved ratio or involved-uninvolved difference) should be considered in assessing response. ***Patients included on the study on the basis of FLC alone (e.g., no measurable serum/urine) should be the only ones who are evaluated using FLC response criteria. The others should follow usual criteria and ignore FLC results.***

- **Evaluable Disease:** Patients who do not have a “measurable” serum M-spike, serum free light chain, or urine M-spike.
- **Oligosecretory Myeloma:** Patient with multiple myeloma who has NEVER had “measurable” serum M-spike or urine M-spike, but has had a detectable monoclonal protein in his/her serum and/or urine and/or measurable serum free light chain.
- **Non-Secretory Myeloma:** Patient with multiple myeloma who has NEVER had a detectable monoclonal protein in his/her serum and/or urine.

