16.3 Phase II Design and Analysis

16.3.1 Primary Endpoint and Estimation:

The primary endpoint is the proportion of patients who have at least a partial response to treatment. Throughout Section 16.3, partial response or better will be considered synonymous with “success”, unless specified otherwise. The 6 patients treated at the recommended dose level (MTD) within each group will be included in the analysis for this portion of the study. The efficacy population will include the 63 patients across groups and include all patients meeting eligibility criteria who signed a consent form and began treatment.

The proportion of successes will be estimated by the number of successes divided by the total number of patients in the efficacy population. Eligible, treated patients who are unevaluable for response will be included in the denominator when estimating the proportion of successes. Confidence intervals for the true success proportion will be calculated according to the properties of the binomial distribution. Secondary analyses include estimation of the proportion of successes with confidence intervals for each group.

16.3.2 Statistical Design:

The largest success proportion where the proposed treatment regimen would be considered ineffective in this population is 40%, and the smallest success proportion that would warrant subsequent studies with the proposed regimen in this patient population is 55%. The following one-stage design based on the binomial distribution uses 63 patients to test the null hypothesis that the true success proportion in a given patient population is at most 40%.

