The success rate of 40% is based on the results of two phase III studies of lenalidomide plus dexamethasone versus dexamethasone alone in relapsed or refractory multiple myeloma (MM-009, North America, 353 patients; MM-010, Europe, Australia, and Israel, 351 patients). The overall response (\geq PR) rates associated with lenalidomide and dexamethasone were 61% and 59.1% in MM-009 and MM-010, respectively, and the overall response rates associated with dexamethasone (plus placebo) were 20.5% and 24% in MM-009 and MM-010, respectively, with a median follow-up of 17.1 months (MM-009) and 16.5 months (MM-010) as reported by Weber et al¹⁹. An additional pooled subgroup analysis was reported by Weber et al¹⁹ investigating renal dysfunction groups. Overall response rate to lenalidomide and dexamethasone was not significantly different between patients with creatinine clearance above 60 ml/min and patients with creatinine clearance below 60 ml/min. However, for 16 patients with creatinine clearance below 30 ml/min, median time to progression and overall survival were significantly shorter than for those with creatinine clearance above 30 ml/min. Further, the median time to progression and overall survival of patients with creatinine clearance below 30 ml/min was significantly greater than patients with creatinine clearance below 30 ml/min on the dexamethasone (and placebo) arm. Results for overall response rate in the <30 ml/min group were not reported. Based on this, it is reasonable to anticipate that the overall response rate in (at least) Group B and Group C of the current study will be less than 60%. However, the study chairs felt that an overall response rate of 40% would be the minimum acceptable in this context.

16.33 Decision Rule: Enter 63 patients into the study. If 30 or fewer successes are observed in 63 eligible, treated patients, we will consider this regimen ineffective in this patient population and terminate this study. If 31 or more successes are observed among 63 eligible, treated patients, we may recommend further testing of this regimen in subsequent studies in this population.

16.34 Over Accrual: If more than the target number of patients are accrued, the additional patients will not be used to evaluate the stopping rule or used in any decision making process but will be included in all final point estimates.

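### Protocol 11.1 allows one mid-course change of serum response marker because the two results disagree, and no rule says how a switched patient counts in the primary analysis

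*Protocol*

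**What the plan says.** **Marker rule (protocol 11.1, M-Protein).** Serum M-protein is measured by SPEP unless SPEP is unavailable or judged unreliable. Three technical examples are listed: a spike in the beta region, a very large narrow spike, and multiple peaks of the same protein. Quantitative immunoglobulin may then be used instead, but this has to be declared at baseline, after which "only nephelometry can be used for that patient to assess response". The section adds that "SPEP derived M-spike values and quantitative nephelometric immunoglobulin values cannot be used interchangeably".

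**The exception (same paragraph).** If, when response is being determined, the immunoglobulin result contradicts the M-spike or the reverse, "the treating physician may request permission from the PI to alter which parameter will be followed for response determination". One such change is allowed per patient.

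**What depends on it.** For serum-measurable patients, Table 11.5 defines PR by a fall of at least 50% in serum M-protein. Protocol 16.3 states: "The primary endpoint is the proportion of patients who have at least a partial response to treatment". The decision rule in 16.33 is: "If 31 or more successes are observed among 63 eligible, treated patients, we may recommend further testing".

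**The SAP.** Section 5.1 refers to protocol Tables 11.2 and 11.5. Section 8.6.1 defines the success proportion, and section 9 plans no changes from the protocol analyses. None of these mentions a patient whose marker was changed.

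**The concern.** The baseline lock and the exception pull in opposite directions. The lock means that the yardstick is chosen before any post-treatment value exists. The exception lets it be changed because of post-treatment values, at the request of a physician who knows both results and treats the patient. Section 11.1 does not restrict the change to its own technical reasons. It also does not say how large a contradiction must be, on what grounds permission is given, whether earlier response calls are revised, or which baseline value the new marker is compared with.

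PR or better is the primary endpoint, so the choice bears directly on whether a patient counts towards 31. Treatment continues until progression (7.11, 7.12), which gives a treating physician a reason to prefer the marker that shows response. Neither document describes central or independent response review. What is at stake is the false-positive rate of the one efficacy decision in the trial.

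**Working it through.** **1. Inputs.** From protocol 16.3: N = 63, one stage; null rate 0.40; alternative rate 0.55; success declared at 31 or more responders.

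**2. Reproduce the plan's table (16.35).** With X ~ Binomial(63, p), the probability of a positive result is P(X ≥ 31).

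| True rate p | Plan | Exact |
|---|---|---|
| 0.40 | 0.09 | 0.0873 |
| 0.45 | 0.29 | 0.2922 |
| 0.50 | 0.60 | 0.5993 |
| 0.55 | 0.85 | 0.8533 |
| 0.60 | 0.97 | 0.9687 |

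The plan's figures are right. The problem is how responders are classified, not the sample-size calculation.

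**3. Which patients can be affected.** The exception covers SPEP M-spike versus quantitative immunoglobulin only. Patients followed by urine, free light chain or marrow alone are outside it. After baseline, immunoglobulins are required only if used to assess response (section 4.0, footnote 3), so not every SPEP-followed patient will have a second result.

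**4. How a case could arise (invented values).** Take a patient with measurable serum but not urine M-protein. The M-spike falls from 2.0 to 1.1 g/dL: (2.0 − 1.1)/2.0 = 45%, short of PR. IgG falls 52%, past the 50% line. If the physician asks, the PI agrees that this is a contradiction, and a second consecutive determination confirms it on IgG, the patient could be recorded as PR. Whether 45% against 52% is a contradiction is open to argument, and 11.1 gives no definition that settles it.

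**5. Sensitivity of the decision rule.** Let k be the net number of non-responders reclassified as responders (favourable minus unfavourable switches). The recorded count is X + k, so the chance of a positive result is P(X + k ≥ 31) = P(X ≥ 31 − k).

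| Net k | Threshold on X | Chance at 0.40 | Chance at 0.55 |
|---|---|---|---|
| −1 | 32 | 0.054 | 0.788 |
| 0 | 31 | 0.087 | 0.853 |
| 1 | 30 | 0.135 | 0.904 |
| 2 | 29 | 0.197 | 0.940 |

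The documents give no discordance or switch rate, so k is an assumption. The rows for k = 1 and 2 are one-sided illustrations; the row for k = −1 shows the opposite direction.

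**6. Does anything downstream close the gap?** Table 11.2 assigns tests by on-study baseline value. It has a SPEP column but none for quantitative immunoglobulin. Table 11.5 defines PR by what was measurable on study. Neither table covers a change of marker, and 11.3 requires two consecutive determinations without saying whether both must be on the same marker. An analyst who reaches a switched patient finds no rule.

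**The case against.** The strongest reply is that the exception is narrow and supervised. It covers one pair of markers, needs PI permission, may be used once per patient, and leaves the two-determination requirement in place. If urine M-protein is also measurable, its PR criterion must be met as well. Switches may be unfavourable, including towards progression. SPEP can be truly unreliable, and a rigid lock would then misclassify patients. Table 11.2 also requires SPEP at each disease measurement visit for serum-measurable patients, so the classification by M-spike should often be recoverable after a change to immunoglobulin.

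Most of this stands, and it limits how often the problem can occur. It does not remove it. Section 11.1 does not say whether the PI is a site investigator or the study chair, and it asks for no review blind to response. Confirmation guards against random error, not against choice of marker. Recoverability helps only if someone plans to use it, and the SAP does not.

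A reader might go further in four ways that the documents do not support:

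- **That responder status is open to choice in every patient.** Applying a 10% reclassification rate to all of the roughly 38 non-responders expected at a 40% rate (63 × 0.60 = 37.8) gives p = 0.40 + 0.60 × 0.10 = 0.46 and a chance of 0.35. That base includes patients whom the clause cannot touch, and the 10% has no source.
- **That switches will be mostly favourable.** This is plausible, given who makes the request, but it is not shown.
- **That the 40% benchmark came from trials without such a choice.** Section 16.32 does not describe marker handling in the cited trials, and it ends by resting 40% on the study chairs' judgement.
- **That the plan names no response parameter at all.** The SAP does point to Tables 11.2 and 11.5. What is missing is the rule for switched patients.

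**Conclusion.** The point holds in this limited form. Section 11.1 contains a stated rule, not merely a gap, that lets the serum marker deciding the primary endpoint be changed because of the results it gave. There are no criteria for approval, and neither 16.3 nor the SAP says how the patient is then classified. This permits selection; nothing in the documents shows that selection took place.

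Its size is unknown because no switch frequency is given. The decision rule is nevertheless sensitive to very few patients: at a true 40% rate, one net favourable reclassification takes the false-positive chance from 0.087 to 0.135, and two take it to 0.197. These figures assume net movement in the favourable direction and otherwise binomial responses. The stated sample size and power are unaffected. The plan should be amended, because the exposure is on the primary endpoint and the remedy is mainly wording.

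**What to change.** **Protocol 11.1, with matching text in SAP 5.1 and 8.6.1:**

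- State that the serum marker designated at baseline determines response in the primary analysis.
- Accept a change of marker for that analysis only for the technical reasons already listed in 11.1, documented from the laboratory report without reference to response status.
- After an accepted change, judge response and confirmation wholly on the new marker, against that patient's own baseline value of it. Quantitative immunoglobulins are already drawn at baseline.
- Do not also require PR on the abandoned marker. A marker accepted as unreliable should not decide the outcome, and a worse-of-two rule would bias the rate downward.
- For every switch, record the date, the reason and both sets of values, and keep measuring the marker that was designated at baseline.

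**SAP outputs:** a listing of all switched patients, and a sensitivity analysis that classifies them by the baseline-designated marker.

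**Cost.** N and the cut of 31 do not change. A few patients with discordant markers but no documented technical reason may count as non-responders. Continuing the baseline-designated marker can mean extra tests, mainly after a change from immunoglobulin to SPEP, since immunoglobulins would then no longer be required.
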